ADDITION TREATMENT OUTCOME MONITORING STUDY

PROTOCOL AND STATISTICAL ANALYSIS PLAN

[name]

Last modified October 14, 2019

MEASURE SCHEDULE

Instrument	Abbrev.	Screen	Baseline	Week 6	Week 12	Week 26
Alcohol Use Disorder Identification Test – Consumption Version	AUDITC	x				
Eligibility criteria, self-report	ELIG	x				
Eligibility criteria, HER	ELIG_EHR	x				
Follow-up cover sheet	FUP		x	x	x	x
Contact information	CONTACT	x	x	x	x	x
Demographics	DEMO		x			
Technology use	TECH		x			
Substances focused on in treatment	SUBSTANCE S		x			
Treatment Goal	TXGOAL		x			
Short Inventory of Problems (Lifetime)	SIPL		x			
Weekly check-in (if not completed remotely)	CHECKIN		x	x	x	x
ASI-LITE (alcohol and drug consumption past 30 days)	ASILITE		x	x	x	x
AUD checklist	AUDCHK		x	x	x	x
SUD checklist	SUDCHK		x	x	x	x
Brief Situational Confidence Questionnaire	SEQ_SUBST ANCE		x	x	x	x
Readiness Rulers	RR		x	x	x	x
Penn Alcohol Craving Scale	PACS		x	x	x	x
PHQ-9	PHQ9		x	x	x	x
Service use	SERVICES		x	x	x	x
Usability of check-in survey	USA_SURVE Y		x	x	x	x
Self-efficacy for check-in survey	SEQ_SURVE Y		x	x	x	x
Working alliance inventory, short form	WAISF		x	x ¹	x ¹	x ¹
Treatment satisfaction	TXSATIS		x	x ¹	x ¹	x ¹
In-session discussion survey	INSESS		x	x ¹	x ¹	x ¹
Audio recording of sessions (if opted in)	AUDIOCONS ENT			x		
Qualitative experiences using ATOM tool	ATOM_EXP			x	x	x
Qualitative experiences being in the study	STUDY_EXP				x	x
EHR measures (completed by RA)	EHR					x
Demographics, clinicians	DEMO_CL		x			
In-session discussion survey, clinicians	INSESS_CL			x ¹		
Dashboard usability, clinicians	USA_CL				x	

White background = complete by patients. Gray background = completed by clinician

¹ = Completed only if the patient has attended treatment at HMHAS since the last completed assessment.

STUDY FLOW - CLINICIANS

Recruitment (clinicians)

- **Clinician** participants will be recruited through verbal announcements at staff meetings and by placing letters inviting them to participate in clinicians' mailboxes.
- The research team will make efforts to recruit clinicians prior to recruiting patients.

Screening and Eligibility (clinicians)

- Eligibility will be extended to all clinicians who are employed within the Addictions Clinic or who are identified as harm reduction therapists for patients with substance use disorders within the Harborview Mental Health and Addictions Services (HMHAS) clinic.

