- To ensure that patients understand the implications of the condition they are assigned to, we will complete the following steps during the consent process. Research staff will show the participant a paper form with a description of both conditions (**blue group** and **green group**) and will circle the condition that the participant was assigned to. The participant will then verbally describe their understanding of that condition assignment to the research staff. When the participant's understanding is adequate, the participant will initial the form to indicate their understanding of the study condition they are in. If the participant is unable to adequately describe the group they are in, the RA will re-describe the conditions and will again ask to confirm the participant's understanding. If the participant is still unable to understand adequately, the participant will be compensated for completing the baseline assessment but will not advance further into the study.

Setup and complete first “weekly check-in” survey

- The RA will describe the “weekly check-in” surveys, which will be sent to patient participants via a personalized REDCap link that is emailed or text messaged to patients through REDCap. The research staff will enter the participant's contact information into REDCap which will then send the participant their first weekly check-in via email or text message. The participant will be asked to complete the check-in during the baseline appointment on their smartphone (if possible) or on a computer in the HMHAS clinic. The RA will help instruct the participant as needed on how to open the survey link, complete the questionnaire, and submit their responses.
- The RA will teach participants how to connect to Harborview's WiFi network (designated for visitors and patients) as needed.
- All participants will then complete the remaining baseline assessment measures.

Assessments

- Participants will complete interviews and questionnaires at baseline and 6, 12, and 24 week follow-ups. All baseline assessments will necessarily occur in person to allow fully informed consent and to initiate the study procedures. Follow-up assessments will occur in person whenever possible, but may occur via telephone and/or via web-based REDCap survey if a participant is unable or unwilling to complete follow-up (however, we will attempt to conduct these in person whenever possible).

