- Assessment questionnaires may be completed on paper-and-pencil forms or entered directly into REDCap by patients via desktop computers in the research office. The questionnaires will be branded with the UW ATOM Study logo to help identify them as part of the study.
- Research staff will compensate patients with a \$50 pre-paid Visa gift card (functionally similar to a debit card) for their participation. We anticipate that most follow-ups will occur in person, allowing the RA to pay participants at the appointment. If a participant completes a follow-up assessment remotely (via telephone or online), we will allow the participant to pick up their gift card in person or offer to mail it via US Postal Service to the participant, with the caveat that we cannot guarantee the gift card will arrive (e.g., it could be stolen if it is delivered to an unsecured location).
- Research staff will give the participant a business card with the name and contact information for their primary point of contact for the study at the end of each in-person assessment.
- Research staff will emphasize that patients may continue to participate in the study even if they discontinue treatment at HMHAS.

Weekly check-in surveys

- Participants will be sent a link to complete weekly check-in surveys once per week up to 24 times after the baseline appointment. Surveys will be sent automatically through REDCap and will use a customized link created by REDCap, which obviates any need to collect identifiers in the longitudinal surveys. Links to weekly check-ins will be sent to participants via text message or email (based on the participant's preference).
- After the 1st and 2nd weekly check-ins, an RA will contact participants via phone, text message, or email to inquire about their experience completing the questionnaire.
 - If the participant completed the questionnaire, the RA will ask about any potential challenges that could be encountered when completing the questionnaires (e.g., was the text large enough to read, were there any questions in the survey that were difficult to understand).
 - If the participant did not complete the questionnaire, the RA will ask about challenges that could have stopped them from completing the questionnaires, and will then attempt to help the participant troubleshoot those problems and encourage completion of the weekly check-in surveys.

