- For the first three months of the study, an RA will proactively reach out to patient participants to assist with completing weekly check-ins if there is evidence of non-completion. For example, if participants do not complete weekly check-ins, the RA will contact the patient to inquire if they are receiving the surveys or unable to complete them (e.g., due to changes in phone number or loss of their personal smartphone).
- For months 4-6, we will evaluate the extent to which participants sustain their engagement with the survey after proactive outreach from RA's has ended. Automated survey reminders will continue to be sent to patients through REDCap, and patients may contact the study team for assistance or to inform us of changes in their contact information. However, RAs will not proactively reach out to patients to encourage or assist with survey completion. The purpose of this phase is to assess the *sustainability* of the tool when there is minimal involvement by the researchers.

Other activities during research period

- Research staff will periodically contact participants via text message, email, or phone to:
 - Schedule and remind participants of upcoming research appointments
 - Coordinate payments for involvement in the research

- Check in regarding potential changes in contact information (e.g., if participant does not respond to surveys or messages sent by staff)
- Research staff will periodically review the participant's electronic health record to check for updated contact information and to assist with scheduling follow-ups (e.g., to help schedule follow-up research appointments with their clinical appointments, which will reduce the burden of making extra trips to Harborview to complete the study assessments).
- Throughout the study, all decisions that are made in therapy sessions, including any medications prescribed, will be decided by clinical staff as part of clinical care. The research team will not prescribe, advise, or provide consultation on such decisions.

Counseling Session Recordings

- If the patient and their participating clinician have both opted-in to recording sessions, then research staff will work with the patient and clinician to set-up materials for audio recording near the 6-week follow-up point.

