 - Prior to the patient's scheduled counseling session, research staff will give their clinician an envelope with a consent form allowing for permission to audio record, (the form will use large, bold font to indicate that both the patient and clinician must both agree to recording on the date that the recording is made and must sign the form prior to the recording). The envelope will also include a digital audio recorder (with any pre-recorded audio wiped from the device) along with instructions on how to use the recorder. Clinicians will be asked to keep these materials in a drawer or cabinet in their office, which per clinic policy must remain locked at all times.
 - Within 2 business days of the completed session, the research staff will retrieve these materials from the clinician. Signed consent forms will be filed and audio recordings will be removed from the recording devices.

EHR Coding – 6 months after baseline

- Research staff will review patients' UW/Harborview electronic health records (via EPIC) for the six-month period after the participant enrolls. EHR data will never be printed or downloaded; it will only be coded using research forms. Direct identifiers will not be recorded on research forms. Research staff will use EHR coding forms to obtain the study information and will then enter information from these forms into REDCap.

DATA ANALYSIS PLAN

- Descriptive statistics, data visualizations, and multilevel models will be used to characterize measures of acceptability and engagement with the intervention with 95% CI's. Statistics on enrollment (e.g., number of patients and clinicians eligible and willing to participate), measure completion, and dashboard use will be used to assess acceptability and engagement.
- Linear regression models will compare participants in the measurement-only (blue group) vs. measurement and feedback (green group) conditions on in-session discussion topics.
- Multilevel models will generate effect size estimates and 95% CIs to examine whether TABLET sessions have differential degrees of changes in weekly progress and measures. Models will be two-level (repeated measures nested within patients); however, the need for three-level models (patients nested within clinicians) will be tested. Fixed effects for study condition and fixed effects for time will be used to generate growth curve models of change over time in each

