TABLET-recorded measure. Growth-curve modeling will allow testing between conditions in the amount of change over time for each construct.

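### Does the plan's silence on random slopes make the confidence intervals from the weekly growth models too narrow?

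*Combined protocol and SAP*

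**What the plan says.** The third bullet of the Data Analysis Plan sets out the multilevel analysis. On structure it says: "Models will be two-level (repeated measures nested within patients); however, the need for three-level models (patients nested within clinicians) will be tested". On the mean model it says: "Fixed effects for study condition and fixed effects for time will be used to generate growth curve models of change over time in each" measure, which it describes as TABLET-recorded, a term not defined in the document. On the target it says: "Growth-curve modeling will allow testing between conditions in the amount of change over time for each construct". That last sentence makes the condition-by-time term the quantity of interest. The plan names no patient-level random effects, no residual covariance and no type of standard error.

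The number of occasions comes from the patient study flow. At the set-up visit, "The participant will be asked to complete the check-in during the baseline appointment". After that, "Participants will be sent a link to complete weekly check-in surveys once per week up to 24 times after the baseline appointment". This gives up to 1 + 24 = 25 weekly records per patient. The Measure Schedule also lists "Weekly check-in (if not completed remotely" as a row at the assessment visits, so a visit can supply a check-in that was not done remotely. Completion is expected to vary. For months 4 to 6 the plan says: "However, RAs will not proactively reach out to patients to encourage or assist with survey completion".

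The Assessments section says: "Participants will complete interviews and questionnaires at baseline and 6, 12, and 24 week follow-ups". The Measure Schedule heads the last column Week 26.

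**The concern.** The bullet mentions time only under fixed effects, and the one structural check it names is whether a clinician level is needed. Read literally, that could describe a model with a patient random intercept and nothing else. Such a model treats every patient in a group as changing at the same rate. If patients in fact change at different rates, the spread of their slopes is part of the uncertainty in the group difference, and the model leaves nearly all of it out. The more often each patient is measured, the worse this gets: the model counts each extra record as new information about the slope difference, when the limit is really the number of patients. Up to 25 check-ins per patient and about 20 patients per group is where the effect would be largest. At stake is the honesty of a promised 95% interval for the difference in change.

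**Working it through.** The documents state no sample size calculation, SD or slope variance, so there is no figure of the plan's own to reproduce. The check asks how large the effect could be under stated assumptions, and then whether the plan's text commits anyone to it.

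**Inputs from the documents.** Blue group: 20 planned (Condition Assignment). Weekly records: up to 25. Assessments at weeks 0, 6, 12 and 24 (Assessments). Interval: 95%.

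**Assumptions.** Green group 20 (40 also tried); residual SD σ = 1; linear change; complete records; no true difference. Write τ for the between-patient SD of 24-week change. The TABLET measures are read as the weekly check-ins.

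**Step 1: spread of the time points**, with time = week/24.
- 25 weekly records: Σ(w − 12)² = 1300, so Sxx = 1300/576 = 2.257.
- Four assessments (mean week 10.5): 110.25 + 20.25 + 2.25 + 182.25 = 315, so Sxx = 315/576 = 0.547.

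**Step 2: formulas for balanced data**, with N patients and T records each.
- True variance of the slope difference = (σ²/Sxx + τ²)(1/n₁ + 1/n₂).
- Variance reported by the intercept-only model = (MS/Sxx)(1/n₁ + 1/n₂), where MS = σ² + (N − 2)τ²Sxx / [N(T − 1) − 2].
- Coverage = 2Φ(1.96 × model SE / true SE) − 1.

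**Step 3: worked case**, τ = 1, 20 per group, 25 records.
- MS = 1 + 38 × 2.257/958 = 1.0895.
- Model SE = √(1.0895/2.257 × 0.1) = 0.220.
- True SE = √((1/2.257 + 1) × 0.1) = 0.380.
- Ratio 0.380/0.220 = 1.73; coverage 74.3%.

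The same formulas across the assumed range:

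| τ | Model SE (25) | True SE (25) | Coverage, 25 weekly | Coverage, 13 evenly spaced | Coverage, 4 assessments |
|---|---|---|---|---|---|
| 0 | 0.210 | 0.210 | 95.0% | 95.0% | 95.0% |
| 0.25 | 0.211 | 0.225 | 93.4% | 94.2% | 94.7% |
| 0.5 | 0.213 | 0.263 | 88.7% | 91.6% | 94.0% |
| 0.75 | 0.216 | 0.317 | 81.8% | 87.6% | 92.8% |
| 1.0 | 0.220 | 0.380 | 74.3% | 82.8% | 91.3% |

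With 20 versus 40 patients, coverage moves by no more than 0.1 point. Simulation with 20,000 trials per setting agrees to within 1 point. It puts the random-slope interval at about 95% coverage throughout, at 1.02, 1.09, 1.27 and 1.77 times the intercept-only width for τ = 0, 0.25, 0.5 and 1.0.

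**Step 4: does the clinician check help?** With complete records, the condition-by-time contrast lies within patients, so a clinician intercept cancels out of it. In 150 simulated fits at τ = 1 with 8 assumed clinicians, the SE was 0.219 with or without a clinician intercept, against an actual SD of 0.371. A patient random slope gave 0.369. This was checked only for a clinician intercept and complete records. The plan does not restrict its third level to an intercept.

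**Step 5: does the plan commit to the intercept-only model?** It does not. Naming fixed effects for condition and time describes the average curves. A random slope is a patient-level deviation around an average time effect, so it needs that fixed effect and is not excluded by it. The two-level structure leaves open which coefficients vary between patients. The stated aim, to compare amounts of change using growth curves, points towards letting individual curves differ.

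**The case for a change.** The strongest case for acting is that two analysts could both follow the bullet faithfully and report different intervals. One could fit an intercept only and the other add a slope, and with full weekly data their widths could differ by a factor of up to about 1.8 at τ = 1. The stated clinician check may look like a safeguard and, for a clinician intercept, is not one. One sentence in the plan would settle the matter.

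The silence is real, the arithmetic is right, and the point about the clinician intercept holds for complete data. But the harm needs two things that the documents do not supply: an analyst who leaves out the slope, and slopes that vary enough to matter. At τ = 0 nothing is lost, and at 0.25 the loss is under 2 points. The 74% figure needs a slope SD as large as the residual SD and every check-in completed.

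Nor does a tighter rule come free. In simulations with patients stopping early, the random-slope fit was singular in 62%, 53%, 36% and 7% of trials at τ = 0, 0.25, 0.5 and 1.0. Patient-clustered, small-sample-corrected standard errors used in every such trial covered 94% to 96%. There is thus more than one sound way to fill the gap, and the choice depends partly on how complete the data turn out to be. Fixing the reported model at two levels would also be a trade-off. With patient and clinician slope SDs both assumed to be 0.5 and 8 clinicians, the two-level random-slope interval covered 95% when clinicians were evenly mixed across groups, 91% to 92% with a 75/25 split, and 80% when separated by group. The plan's own test for a clinician level leaves room to deal with that.

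**Conclusion.** The concern does not call for a change. The plan leaves the patient-level random part unstated, but it states no wrong rule, and an analyst fitting two-level growth curves to weekly data would ordinarily consider random slopes or use standard errors clustered by patient.

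If that were not done, the cost for complete weekly data would run from nothing to about 21 points of coverage (95.0% − 74.3%) as τ goes from 0 to 1.0. It would be at most about 4 points (95.0% − 91.3%) for measures taken at four assessments. These figures rest on σ = 1, linear change, 20 per group and complete records, and on reading the TABLET measures as the weekly check-ins. None of these slope variances comes from the documents.

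The setting also limits what is at stake. Allocation is non-random and mostly by order of entry, so a difference in change between groups is open to confounding by calendar time and clinician, whatever the interval's width.

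The final assessment, headed Week 26 in the Measure Schedule and described as 24 weeks in the Assessments section, is a clerical mismatch to be reconciled. It alters nothing in this conclusion.
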